3.3.4.2 Discontinuation of the trial by the sponsor

Boehringer Ingelheim (BI) reserves the right to discontinue the trial overall or at a particular trial site at any time for the following reasons:

- 1. Failure to meet expected enrolment goals overall or at a particular trial site
- 2. Emergence of any efficacy/safety information invalidating the earlier positive benefit-risk-assessment that could significantly affect the continuation of the trial
- 3. Violation of GCP, the CTP, or the contract, disturbing the appropriate conduct of the trial

The investigator/the trial site will be reimbursed for reasonable expenses incurred in case of trial termination (except in case of the third reason).

Proprietary confidential information © 2017 Boehringer Ingelheim International GmbH or one or more of its affiliated companies

4. TREATMENTS

4.1 TREATMENTS TO BE ADMINISTERED

The trial medication will be provided from NBI.

4.1.1 Identity of BI investigational product(s) and comparator product(s)

The characteristics of test product 1 are below.

Substance: Empagliflozin

Pharmaceutical form: film-coated tablet

Source: Boehringer Ingelheim

Unit Strength: 10 mg

Route of administration: oral, once daily

The characteristics of test product 2 are below.

Substance: Empagliflozin

Pharmaceutical form: film-coated tablet

Source: Boehringer Ingelheim

Unit Strength: 25 mg

Route of administration: oral, once daily

The characteristics of the reference product placebo 1 are below.

Substance: Placebo matching empagliflozin 10 mg

Pharmaceutical form: film-coated tablet

Source: Boehringer Ingelheim

Unit Strength: -

Route of administration: oral, once daily

The characteristics of the reference product placebo 2 are below.

Substance: Placebo matching empagliflozin 25 mg

Pharmaceutical form: film-coated tablet

Source: Boehringer Ingelheim

Unit Strength: -

Trial Protocol

Page 33 of 73

Proprietary confidential information © 2017 Boehringer Ingelheim International GmbH or one or more of its affiliated companies

Route of administration: oral, once daily

4.1.2 Method of assigning patients to treatment groups

After the patient's eligibility has been confirmed, the patient will be assigned to placebo at Visit 6 and randomly assigned to either empagliflozin 10 mg plus placebo or empagliflozin 25 mg plus placebo (1:1 ratio) at Visit 7 via Interactive Response Technology (IRT) (see Section 4.1.4). To facilitate the use of the IRT, the investigator will receive all necessary instructions.

Patient assignment to the treatment groups will be determined by a computer generated random sequence. Access to the randomisation code will be controlled and documented – for further details please see Sections 4.1.5.1 and 4.1.5.2.

The assigned medication number will be entered in the eCRF, and the corresponding medication kit should be given to the patient. Using this procedure, relevant parties will be blinded to the treatment group assignment.

4.1.3 Selection of doses in the trial

The selected doses of empagliflozin are based on the approved and marketed doses in Japan. Approximately 50% of the patients will receive empagliflozin 25 mg without starting lower dose of empagliflozin 10 mg although the Japanese label defines the starting dose of empagliflozin 10 mg. Empagliflozin 25 mg as well as 10 mg were used in the phase III clinical trials as for the expected therapeautic doses and both empagliflozin doses were well tolerated as initial dosage.

4.1.4 Drug assignment and administration of doses for each patient

The treatments to be evaluated are outlined in Table 4.1.4: 1 below. Patients who are qualified will be randomised to one of the dosage and treatment schedules described below. Medication will be dispensed in a double-blind and double-dummy fashion.

All patients will be assigned to a placebo run-in kit at the beginning of the placebo run-in period (Visit 6), and dispensing will be done just once. Dispensing of kits for the double-blind treatment period will begin at Visit 7. Dispensing will be done on 8 occasions over a period of 52 weeks (i.e. every 4 weeks in Visit 7 to Visit 10; every 8 weeks in Visit 11 to Visit 14). Patients will receive empagliflozin as trial medication. However, background medication will not be dispensed as trial medication. Therefore, background medication (liraglutide) will be prescribed at each clinical site. For details regarding packaging (e.g. number of tablets per container), please see Section 4.1.6.

c03122586-03

Proprietary confidential information © 2017 Boehringer Ingelheim International GmbH or one or more of its affiliated companies

Table 4.1.4: 1 Empagliflozin, oral administration per dose group and day

Dose group	Empagliflozin	Empagliflozin	Total units	Timing
	10 mg	25 mg	per dose	
	C	S	1	
Placebo run-in period				
(open label)				
All patients	Matching placebo	Matching placebo	2 tablets	Once daily,
•				Morning
Treatment period				
Empagliflozin	Active drug	Matching placebo	2 tablets	Once daily,
10 mg	S	C 1		Morning
C	M. (1' 1 1	A - 4' 1	2 . 11 .	0 1.1-
Empagliflozin	Matching placebo	Active drug	2 tablets	Once daily,
25 mg				Morning

Placebo run-in period (open label):

From the start of the placebo run-in period, patients should be instructed to take their trial medication once daily with water. The medication should be taken at the same time every day. If a dose is missed by more than 12 hours, that dose should be skipped and the next dose should be taken as scheduled.

Double-blind period:

During the treatment period, patients should be instructed to take their trial medication once daily with water. To ensure a dose interval of about 24 hours, the medication should be taken at the same time every day. If a dose is missed but the patient is aware of missing the trial medication within 12 hours from planned intake, the dose should be taken immediately, and if a dose is missed by more than 12 hours, that dose should be skipped and the next dose should be taken as scheduled. On days before the next visit, the dose should be taken 22-26 hours before the planned dose at the visit. No double doses should be taken. Empagliflozin can be taken with or without food.

The dosage and usage of background medication should remain unchanged during the double-blind treatment period (see Section 4.2.1).

Patients should be instructed not to take their trial medication in the morning of study visits as they will be dosed while in the study site. Patients who fail to do so should have the visit rescheduled as soon as possible, ideally on the following day. Patients are asked to bring their trial medication to the sites from. Visits should be routinely scheduled in the morning, at approximately the same time of day for each visit. The actual date and time of administration of the medication at the trial visit will be recorded in the eCRF.

Page 35 of 73

Proprietary confidential information © 2017 Boehringer Ingelheim International GmbH or one or more of its affiliated companies

4.1.5 Blinding and procedures for unblinding

4.1.5.1 Blinding

Trial medication during run-in period will be open-labelled.

After randomisation at Visit 7, patients, investigators and everyone involved in trial conduct or analysis or with any other interest in this double-blind study will remain blinded with regard to randomised treatment assignments until database lock. To achieve all dose combinations and to ensure blinding, empagliflozin and placebo tablets are combined in double-dummy fashion as shown in Table 4.1.4: 1 and patients will have to take two tablets for each dose.

However, due to the requirements to report suspected serious unexpected adverse reactions (SUSARs), it may be necessary for a representative from BI's drug safety group to access the randomisation code for individual patients during study conduct. In such cases, access to the code will only be permitted by authorised drug safety representatives. Access to the code will be via the IRT.

The randomisation code will be kept secret by Clinical Trial Support up to database lock. Please see Section 4.1.5.2 for the rules regarding breaking the code for an individual or for all patients in emergency situations.

4.1.5.2 Unblinding and breaking the code

In this blinded trial, an emergency code break will be available to the investigator via IRT system. This code break may only be accessed in emergency situations when the identity of the trial drug must be known to the investigator in order to provide appropriate medical treatment or if required to assure the safety of trial participants. Each site receives a manual from the IRT provider that contains instructions on how to unblind the treatment of a patient via the IRT (via 24-hour Emergency helpline). If the code break for a patient is accessed, the sponsor must be informed immediately. The reason for accessing the code break, together with the date, must be documented on the appropriate eCRF page. In case third party needs to break the code, however, when the investigator cannot be reached, the code can be opened by calling emergency code manager (see Emergency Code Break Manual) in the ISF.

4.1.6 Packaging, labelling, and re-supply

Study medication will be provided by BI.

The study medication will consist of containers labelled with the trial identification and medication kit number. Each kit will contain an appropriate number of empagliflozin tablets or matching placebo tablets with some reserve (see below), for dosing until the next scheduled visit.

The placebo run-in kit, assigned to all patients successfully completing Visit 6, will contain 42 tablets in a wallet (i.e., sufficient supply for 2-week administration, with supply for 1-week administration in reserve). One kit type (wallet) will be used for the double-blind treatment either 4 weeks or 8 weeks interval. Wallet will contain 84 tablets (i.e., sufficient supply for 4-week administration, with supply for 2-week administration in reserve). When patients are in the 4 weeks interval at Visits 7, 8, and 9, they will receive one wallet. When patients are in the 8 weeks interval at Visit 10, 11, 12, 13 and 14, they will receive 2 wallets. The total number of tablets dispensed to a patient during the double-blind treatment period will therefore be 1092 at a maximum.

Supply and re-supply will be managed by IRT.

For details of packaging and the description of the label, refer to the ISF.

4.1.7 Storage conditions

Drug supplies will be kept in their original packaging and in a secure limited access storage area according to the recommended storage conditions on the medication label. A temperature log must be maintained for documentation.

If the storage conditions are found to be outside the specified range, the local clinical monitor (as provided in the list of contacts) must be contacted immediately."

4.1.8 Drug accountability

The investigational drug storage manager will receive the investigational drugs delivered by the sponsor when the following requirements are fulfilled:

- · Approval of the trial protocol by the IRB / ethics committee,
- · Availability of a signed and dated clinical trial contract between the Sponsor and the head of the investigational site,
- · Approval/notification of the regulatory authority, e.g. competent authority,
- · Availability of the curriculum vitae of the principal Investigator,
- · Availability of a signed and dated clinical trial protocol

The investigational drug storage manager must maintain records of the product's delivery to the trial site, the inventory at the site, the use by each patient, and the return to the sponsor or alternative disposal of unused products.

These records will include dates, quantities, batch / serial numbers, expiry ('use- by') dates, and the unique code numbers assigned to the investigational product and trial patients. The investigational drug storage manager will maintain records that document adequately that the patients were provided the doses specified by the CTP and reconcile all investigational products received from the sponsor. At the time of return to the sponsor and/or appointed CRO, the investigational drug storage manager must verify that all unused or partially used

drug supplies have been returned by the clinical trial patient and that no remaining supplies are in the Investigator's possession.

Back ground medication:

One auxiliary Medicinal Products (AMPs) accountability form will be provided for liraglutide to the trial site. This record will include dates, quantities, batch / serial numbers, expiry ('use-by') dates and unique code numbers to the investigational product and trial patients.

4.2 CONCOMITANT THERAPY, RESTRICTIONS, AND RESCUE TREATMENT

Details of all concomitant therapy during the clinical trial will be recorded on the appropriate pages of the eCRFs.

4.2.1 Rescue medication, emergency procedures, and additional treatment(s)

Throughout the duration of the trial, patients should continue to take background therapy, the dose of which should remain unchanged if at all possible (for further details see below). This background medication will not be provided as part of the clinical trial supplies. Only the liraglutide is allowed to be used as GLP-1 RA background medication.

The use of antidiabetic agents other than liraglutide and the allocated medication after randomisation (Visit 7) will be prohibited during the course of the study.

In case of conditions that may lead to fluid loss (e.g. gastrointestinal illness), careful monitoring of volume status (e.g. physical examination, blood pressure measurements, laboratory tests including haematocrit) and electrolytes is recommended for patients receiving empagliflozin. Temporary interruption of treatment with empagliflozin should be considered until the fluid loss is corrected.

In the case of hypoglycaemia that may put the patient at risk (e.g. repeated symptomatic hypoglycaemia or severe hypoglycaemia), appropriate dose adjustment of liraglutide, such as a dose reduction/discontinuation, should be initiated.

If, in the investigator's clinical consideration, the patient's hyper- or hypoglycaemia cannot be controlled, the patient should be discontinued from the trial as specified in Section 3.3.4.

Special attention must be paid to the prevention of DKA. All patients must be made aware of this risk and need to be instructed to contact the Investigator or other healthcare professional in case of symptoms of DKA. For further details see Section 2.3.

In case of a suspected DKA the Investigator should ensure that appropriate tests are performed at the earliest opportunity according to guidelines in Japan, such as a blood gas test (i.e. pH, bicarbonate anion gap, potassium, blood glucose, etc; the results will be

collected on the relevant page of the eCRF) and that the patient is appropriately treated (i.e. hospitalized or referred to emergency treatment) according to treatment guidelines in Japan.

Any additional treatment which is considered necessary for the patient's welfare may be given at the discretion of the investigator. Exceptions to this are the restrictions described in Section 4.2.2.

There are no special emergency procedures to be followed.

4.2.2 Restrictions

4.2.2.1 Restrictions regarding concomitant treatment

The use of antidiabetic agents other than liraglutide and the allocated study drugs after randomisation will be prohibited during the course of the study.

Short-term use of insulin will be permitted (only in the event of an emergency situation and/or hospitalisation) based on clinical judgement of the investigator or treating physician. Prolongation of such insulin treatment over more than 2 weeks vs. treatment discontinuation should be discussed on a case-by-case basis between the investigator and the TCM.

Additionally, treatment with anti-obesity drugs or systemic steroids will be prohibited due to their influence on glucose metabolism. However, one off or short-term use (i.e. ≤ 2 weeks duration) of systemic steroids will be permitted as well as therapy with non-systemic steroids such as inhaled or local steroids. Furthermore, for patients taking thyroid hormones, any change in the dose should be avoided. If dose changes occur, they should be recorded in the source documents and in the eCRF.

The risk of volume depletion may be increased in a patient treated with diuretic in addition to SGLT-2 inhibitor. Therefore, the co-administration of diuretic had to be avoided if there are not sufficient reasons to use these drugs according to the investigators' clinical judgement.

4.2.2.2 Restrictions on diet and life style

Patients will receive diet and exercise counselling by a diet specialist or trained staff member throughout the duration of the study. The counselling should be based on the diet and exercise recommendation of the Japanese diabetes society. In principle, the contents of diet and exercise should not be changed through the study period. Patients keep record (food intake diary) of the actual food intake over a time of 3 consecutive days in the week before the actual clinic visit and bring the diary at each visit. The patients will be reminded to follow the agreed diet and exercise plan at every visit. An investigator will check compliance with the diet and exercise therapy based on the records of the food intake diary and also by interview with patients.

20 JAN 2017

Trial Protocol

Page 39 of 73

Proprietary confidential information © 2017 Boehringer Ingelheim International GmbH or one or more of its affiliated companies

SGLT-2 inhibitor has a diuretic action and the patients may show signs or symptoms of dehydration. Therefore, the investigator should instruct the patients to drink appropriate volume of water or other drinks every day.

Patients also should not take any investigational drug in other trials within the last 30 days before the date of informed consent for this trial.

There are no other restrictions on diet and lifestyle.

4.2.2.3 Restrictions regarding women of childbearing potential

Women of child-bearing potential must continue to practice an acceptable method of birth control (in accordance with the trial exclusion criteria Section 3.3.3) throughout the duration of the study.

4.3 TREATMENT COMPLIANCE

Patients are requested to bring all remaining trial medication including empty package material when attending visits.

Based on tablet counts, treatment compliance will be calculated as the number of tablet taken, divided by the number of tablet which should have been taken according to the scheduled period, multiplied by 100. Compliance will be verified by the on-site monitor authorised by the Sponsor.

Treatment compliance (%) =
$$\frac{\text{Number of tablet actually taken} \times 100}{\text{Number of tablet which should have been taken}}$$

If the treatment compliance is not between 80-120%, site staff will explain the patient the importance of treatment compliance.

5. VARIABLES AND THEIR ASSESSMENT

5.1 TRIAL ENDPOINTS

5.1.1 Primary Endpoint(s)

The primary endpoint of the trial is the proportion of patients with drug-related adverse events (AE) during 52 weeks of treatment with empagliflozin as add-on to GLP-1 RA (i.e. liraglutide).

5.1.2 Secondary Endpoint(s)

The secondary endpoint is a change in HbA1c from baseline after 52 weeks of treatment of empagliflozin as add-on to GLP-1 RA (i.e. liraglutide).

c03122586-03

[figure not shown]
Proprietary confidential information © 2017 Boehringer Ingelheim International GmbH or one or more of its affiliated companies

5.2 ASSESSMENT OF EFFICACY

HbA1c:

Blood samples for the determination of HbA1c at the central laboratory will be taken. At the screening visit 1, the blood sample can be taken at any time in non-fasted state. At all other visits, the blood samples should be drawn before breakfast and before trial drug administration. The samples will be analysed at a central laboratory having a National Glycohaemoglobin Standardization Program (NGSP) Level I certificate. Further details about sample handling, shipment, and assay procedures can be found in the ISF (Lab manual).

5.3 ASSESSMENT OF SAFETY

5.3.1 Physical examination

A complete physical examination (including cardiac, neurological, dermatological, pulmonological) will be performed by the investigator as described in the Flow Chart. Documentation of, and findings from the physical examination, must be part of the source documents available at the site.

5.3.2 Vital Signs

The seated pulse rate (electronically or by palpation, count for 1 minute) will be measured as described in the Flow chart. Further details on the procedure for seated pulse rate measurements are given in Appendix 10.1.

5.3.3 Safety laboratory parameters

All safety laboratory samples (except at Visit 1) will be collected after a full overnight fast (nothing to eat or drink except water for at least 10 hours) and before the investigational drug is taken as described in the Flow chart and Section 6. The blood sample at Visit 1 (screening visit) can be taken with the patient in a fasted or non-fasted state.

All parameters that will be determined during the trial conduct are listed in Tables 5.3.3: 1 and 5.3.3: 2. The analysis will be performed by a central laboratory. The respective reference range and details about sample handling and shipment will be provided in the ISF (Lab Manual).

Reduced safety lab panels are planned for the following visits:

- For the screening Visit 1, laboratory only includes HbA1c, FPG, liver transaminases (i.e. AST and ALT), ALP, serum creatinine, thyroid stimulation hormone (TSH) and urinalysis.
- FFA and Ketone bodies will be performed as described in the Flow chart.
- Bone markers iPTH (intact parathyroid hormone), 25OH Vitamin D, NTx in urine: planned as described in the Flow chart.
- Only blood sampling for haematology and urine dipstick test will be performed as described in the Flow chart.

Table 5.3.3: 1

c03122586-03

Safety laboratory parameters – whole blood, serum or plasma

Haematology

- Haematocrit
- Haemoglobin
 - Reticulocyte count (reflex test if Hb outside normal range)
- RBC/Erythrocytes
- WBC/Leukocytes
- Platelet count/Thrombocytes
- Differential automatic (relative and absolute count): Neutrophils, eosinophils, basophils, monocytes, lymphocytes

Clinical chemistry

- Albumin
- ALP
- γ-GT (gamma-glutamyl transferase)

(reflex test triggered by elevated ALP on two sequential measures)

- ALT (alanine aminotransaminase, SGPT)
- AST (aspartate aminotransaminase, SGOT)
- Bicarbonate
- Bilirubin total, fractionated if increased
- Calcium
- Chloride
- Creatinine
- Creatine kinase (CK)
- CK-MB, troponin (reflex tests if CK is elevated)
- Lactate dehydrogenase (LDH)
- Lipase
- Magnesium
- Phosphate
- Potassium
- Protein total
- Sodium
- TSH (only at Visit 1)
- Urea (BUN)
- Uric acid
- Cholesterol (total)
- HDL cholesterol
- Calculated LDL cholesterol
- Triglycerides (reflex test for direct measurement of LDL cholesterol triggered if triglycerides are >400 mg/dL or 4.52 mmol/L)

Page 44 of 73

Proprietary confidential information © 2017 Boehringer Ingelheim International GmbH or one or more of its affiliated companies

Safety laboratory parameters – whole blood, serum or plasma

(continued)

Bone Marker (only at selected visits)

iPTH

Table 5.3.3: 1

- 25OH Vitamin D
- NTx in Urine

FFA and Ketone bodies (only at selected visits)

- Total ketone body
- Acetoacetic acid
- 3-hydroxybutyric acid
- Free fatty acid (FFA)

Table 5.3.3: 2 Safety laboratory parameters – urine

Urinalysis

Semi quantitative (dipstick)

- Nitrite*
- Protein
- Ketone
- Urine pH
- Leukocyte esterase (for WBC)*

Quantitative

- Albumin
- Creatinine

Microscopic analysis

Will be performed as reflex test if any of the semi quantitative tests/dispsticks are abnormal:

- Urine RBC/Erythrocyte
- Urine WBC/Leukocytes
- Urine sediment microscopic examination
- Urine culture (including antibiogram test):
 - reflex test triggered by positive leukocyte esterase (for WBC) and/or nitrite in the semi-quantitative test/dipstick

Albumin/creatinine ratio in spot urine will be calculated at the central lab.

Glomerular filtration rate

The eGFR will be derived from serum creatinine values for Japanese equation: eGFR (mL/min/1.73m²) = 194 x [Screatinine (mg/dL)]^{-1.094} x [age]^{-0.287} x [0.739 if patient is female]

Renal function impairment will be classified in the following way:

- No renal function impairment: eGFR >90 mL/min/1.73m²;
- Mild renal function impairment: eGFR 60 to <90 mL/min/1.73m²;
- Moderate renal function impairment: eGFR 30 to <60 mL/min/1.73m²;
- Severe renal function impairment: eGFR <30 mL/min/1.73m².

^{*} Nitrite and leukocyte esterase (for WBC) will be determined both locally on site (not recorded in eCRF) and via central lab. A positive result at site triggers the sampling of mid-stream urine for urine culture.

These classes of renal impairment will be the basis for stratification of subgroup analysis.

Pregnancy testing

Pregnancy testing (urine) will be performed in female patients of child bearing potential only according to the time points indicated in the flow chart.

Criteria for hypoglycaemic events

Every episode of glucose concentrations ≤70 mg/dL (3.9 mmol/L) should be documented in the eCRF with the respective time and date of occurrence. Any hypoglycaemia with glucose concentrations <54 mg/dL (<3.0 mmol/L) and all symptomatic and severe hypoglycaemias should be documented as an AE "hypoglycaemic event".

For the analysis, all hypoglycaemias will be classified according to the following criteria:

- Asymptomatic hypoglycaemia: event not accompanied by typical symptoms of hypoglycaemia but with a measured glucose concentrations ≤70 mg/dL (3.9 mmol/L)
- Documented symptomatic hypoglycaemia with glucose concentrations ≥54 mg/dL and ≤70 mg/dL (≥3.0 mmol/L and ≤3.9 mmol/L): event accompanied by typical symptoms of hypoglycaemia
- Documented symptomatic hypoglycaemia with glucose concentrations <54 mg/dL (<3.0 mmol/L): event accompanied by typical symptoms of hypoglycaemia but no need for external assistance
- Severe hypoglycaemic episode: event requiring the assistance of another person to actively administer carbohydrate, glucagon or other resuscitative actions

Follow-up on suspicion for urinary tract infections

Patients having a history of chronic/recurrent urinary tract infections (UTIs) or genital tract infections (GTIs) or an acute episode of UTI or GTI at screening will be identified and this condition has to be documented as medical history or baseline condition in the eCRF, respectively.

For documentation of acute urinary tract infections during trial conduct, the following measures have to be taken:

- In any case of suspected UTI (symptomatic or asymptomatic) a urine culture sample has to be taken and sent to the central lab for confirmation of the diagnosis (including antibiogram).
- To be able to identify asymptomatic UTIs immediately, a dipstick-test (leukocyte esterase [for WBC] and Nitrite) will be performed at the site at each safety visit with urinalysis. In case of a positive result at site, a urine culture sample has to be taken and sent to the central lab for confirmation of the diagnosis (including antibiogram).

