**4. CHANGES IN THE PLANNED ANALYSIS OF THE STUDY**

No changes in the planned analysis.

[figure not shown]

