#### 7.8.1.4 Analysis of hypoglycaemic events

The investigator will record for each AE whether it represents a hypoglycaemic event and, if so, record additional information to assess the intensity of the hypoglycaemic event as described in CTP, Section 5.3.3. On the basis of this information the hypoglycaemic event will be classified as:

- asymptomatic hypoglycaemia: event not accompanied by typical symptoms of hypoglycaemia but with a measured plasma glucose concentration  $\leq 3.9$  mmol/L (70 mg/dL),
- documented symptomatic hypoglycaemia with a measured plasma glucose concentration  $\geq 3.0$  mmol/L and  $\leq 3.9$  mmol/L ( $\geq 54$  mg/dL and  $\leq 70$  mg/dL): event accompanied by typical symptoms of hypoglycaemia,
- documented symptomatic hypoglycaemia with a measured plasma glucose concentration  $< 3.0$  mmol/L ( $< 54$  mg/dL): event accompanied by typical symptoms of hypoglycaemia but no need for external assistance,
- severe hypoglycaemic episode: event requiring the assistance of another person to actively administer carbohydrate, glucagon or other resuscitative actions.
- symptomatic hypoglycaemia and plasma glucose concentration  $> 3.9$  mmol/L (70 mg/dL)
- symptomatic hypoglycaemia and plasma glucose concentration not measured

The frequency of patients with hypoglycaemia according to investigator's judgement will be summarised by primary SOC and PT.

Confirmed hypoglycaemic AE is defined as hypoglycaemic AE with glucose value available and below 70 mg/dL or where assistance is required.

Summaries of confirmed hypoglycaemic AEs will include total number of hypoglycaemic AEs (asymptomatic and symptomatic), severity and intensity of the worst episode, action taken, minimum glucose level of worst episode, time to onset of first episode, and number of episodes per patient (asymptomatic and symptomatic).

Subgroup analyses of hypoglycaemic AEs with respect to age category, rescue therapy and renal function will be performed.

Summary table will include rate of confirmed hypoglycaemic AEs by severity, by age categories, and by renal function. For subgroup of age categories and renal function, time at risk for each group will be used.

Time to the onset of the first hypoglycaemia will be analysed by Kaplan-Meier estimates. The Kaplan-Meier analysis will be performed based on confirmed AEs.

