Different summaries will be shown for the number of patients with hypoglycaemia (symptomatic, asymptomatic reported as AE, or asymptomatic reported as non-AE), severity of the worst episode, minimum glucose level of worst episode, time to onset of first episode, and number of episodes per patient in the CTR, Appendix 16.1.9.2.

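### The SAP's main hypoglycaemia classes and confirmed-event outputs count asymptomatic episodes of 54 to <70 mg/dL only where a site chose to report an AE

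*Protocol*

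**What the plan says.** Protocol 5.3.3 sets a documentation rule and a narrower AE rule. Documentation: "Every episode of glucose concentrations ≤70 mg/dL (3.9 mmol/L) should be documented in the eCRF with the respective time and date of occurrence". AE reporting: "Any hypoglycaemia with glucose concentrations <54 mg/dL (<3.0 mmol/L) and all symptomatic and severe hypoglycaemias should be documented as an AE". It then states the scope of the analysis: "For the analysis, all hypoglycaemias will be classified according to the following criteria". The first class listed there is asymptomatic hypoglycaemia with a measured glucose of 70 mg/dL or less. Symptomatic events are split at 54 mg/dL; asymptomatic events are not.

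SAP 7.8.1.4 starts from AE records: "The investigator will record for each AE whether it represents a hypoglycaemic event". The classes are assigned from that information, and the asymptomatic class again runs up to 70 mg/dL. A confirmed hypoglycaemic AE is one with a glucose value below 70 mg/dL or a need for assistance. Rates by severity, age category and renal function use confirmed hypoglycaemic AEs. The subgroup analyses are of hypoglycaemic AEs. For time to first event, "The Kaplan-Meier analysis will be performed based on confirmed AEs".

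The same SAP section ends with summaries for CTR Appendix 16.1.9.2 that count patients with any hypoglycaemia ("symptomatic, asymptomatic reported as AE, or asymptomatic reported as non-AE"). SAP Section 4 states: "No changes in the planned analysis".

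**The concern.** The protocol's analysis scope is all recorded episodes. The scope of the SAP's main tables is AEs, yet they carry over a class label, asymptomatic up to 70 mg/dL, that fits the wider scope. Between 54 and 70 mg/dL without symptoms, nothing requires an AE and nothing forbids one. Protocol 5.3.6.1 allows an abnormal laboratory finding to be an AE, and Protocol 5.3.7 leaves the clinical relevance of laboratory changes to the investigator. The same reading can thus be a confirmed event at one site and absent from the confirmed tables at another.

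Hypoglycaemic adverse events are a named safety criterion in the protocol synopsis. What is at stake is whether a reader can interpret the confirmed rate and the time-to-first-event curve. If sites report only what is required, the asymptomatic class holds only values below 54 mg/dL despite its label. If some sites report more, it mixes required with discretionary reports, and the unsplit class does not show which case applies.

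**Working it through.** The documents state no hypoglycaemia rate, so there is no figure of the plan's own to reproduce. The check takes each kind of episode through the AE rule and classes (Protocol 5.3.3) and the confirmed-AE rule (SAP 7.8.1.4).

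| Episode (glucose in mg/dL) | AE required? | Class | In the confirmed-AE outputs? |
|---|---|---|---|
| Asymptomatic, <54 | Yes | Asymptomatic | Yes |
| Asymptomatic, 54 to <70 | No | Asymptomatic | Only if the site reports an AE |
| Asymptomatic, exactly 70 | No | Asymptomatic | No, even if reported as an AE |
| Symptomatic, <54 | Yes | Symptomatic <54 | Yes |
| Symptomatic, 54 to <70 | Yes | Symptomatic 54 to 70 | Yes |
| Symptomatic, exactly 70 | Yes | Symptomatic 54 to 70 | No |
| Severe (assisted) | Yes | Severe | Yes |

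The second row is the gap. The two rows at exactly 70 show a separate, small mismatch: the classes include 70 mg/dL and the confirmed definition excludes it.

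The data for the missing episodes exist. Protocol 5.3.3 requires date and time in the eCRF for every episode up to 70 mg/dL, and Protocol 5.3.5 has the single SMBG value entered in case of hypoglycaemia.

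**Illustration by patient (assumed rates).** Let 10% of patients have at least one mandatory-AE event that meets the confirmed definition. Let a proportion e have an asymptomatic episode of 54 to <70 mg/dL, independently of the first. If none of the latter are reported as AEs, the confirmed proportion is 10%. If all are, it is 1 − (1 − 0.10)(1 − e):

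- e = 5%: 1 − 0.90 × 0.95 = 14.5%
- e = 10%: 1 − 0.90 × 0.90 = 19.0%
- e = 15%: 1 − 0.90 × 0.85 = 23.5%
- e = 20%: 1 − 0.90 × 0.80 = 28.0%

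In an arm of 32 that is 3.2 expected patients against 4.6 (32 × 0.145) to 9.0 (32 × 0.28).

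**Illustration by episode (assumed counts).** Take 5 mandatory-AE episodes with 5, 10 or 20 asymptomatic episodes of 54 to <70 mg/dL. With none of the latter reported as AEs, the confirmed-AE tables hold 5/10 = 50%, 5/15 = 33% or 5/25 = 20% of all episodes. With all reported, they hold 100%.

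**The case against.** The strongest reply is that the SAP already deals with these episodes. Its appendix summaries name asymptomatic episodes reported as non-AEs and cover severity and minimum glucose of the worst episode, time to first episode, and episodes per patient. This stands to a large extent: no recorded episode is lost from the report. It does not repair the main classes, the confirmed rates, the subgroup results or the Kaplan-Meier curve, because the appendix summaries have no stated rate, subgroup or Kaplan-Meier counterpart. They also show that asymptomatic episodes were expected to arrive both as AEs and as non-AEs, while the main tables have no rule for the mix.

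A second reply is that the outputs are labelled as AE outputs, which matches the synopsis criterion. That also stands. A reader might infer that the confirmed rates are undercounts. They fall short only if read as rates of all glucose values below 70 mg/dL, which their label does not claim.

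Third, a reader might infer that differing site practice adds noise to the comparison of arms. The documents do not support this. Counting more events raises the binomial variance whether or not reporting clusters by site, and uniform full reporting would raise it most. Reporting is double-blind, so a systematic difference between arms is not expected either.

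Fourth, the analysis is descriptive with no hypothesis test, and Protocol 2.3 considers the hypoglycaemia risk low. This limits the consequence but does not make the class label accurate.

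**Conclusion.** The point holds for the main hypoglycaemia classes and the AE-based outputs of SAP 7.8.1.4. There, asymptomatic episodes of 54 to <70 mg/dL are counted at the site's discretion, and the main classification is narrower than the scope in Protocol 5.3.3 although the SAP declares no change. Symptomatic, severe and <54 mg/dL events are not affected by this reporting gap.

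The range of 10% against 14.5% to 28% shows how far the confirmed proportion could depend on reporting practice. It rests wholly on assumed rates and is not a forecast.

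A reader might also infer that the primary endpoint is affected. That would need a discretionary AE in an asymptomatic patient, judged drug-related, in someone with no other drug-related AE. Nothing in the documents indicates how often this would happen, so the link is speculative. This is a correction to make in the SAP; it does not threaten the trial's main conclusions.

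**What to change.** In SAP 7.8.1.4:

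- Derive the classification from all episodes recorded in the eCRF, AE and non-AE, as Protocol 5.3.3 states.
- Split the asymptomatic class at 54 mg/dL, so that mandatory and discretionary reports can be told apart.
- Keep the confirmed-AE table. Add the rate and the Kaplan-Meier analysis restricted to events whose AE reporting is mandatory: symptomatic with low glucose, any value below 54 mg/dL, or assisted.
- Reconcile the confirmed definition, which excludes 70 mg/dL, with the classes, which include it.

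The cost is SAP wording and a little more programming; no new data are needed. The downside is one further output that will differ from the confirmed-AE table and needs a footnote to explain why.
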